3.3.3. Exploratory/Other Analyses

Pharmacokinetic and pharmacodynamic analyses will be provided by the outside laboratory.

3.4. Analysis of Safety and Tolerability

All safety endpoints will be summarized using descriptive statistics and will be based on the safety analysis for all patients in Phase 1 dose escalation phase and for patients in Phase 2a expansion phase by disease cohort.

3.4.1. Study Drug Administration

Total duration of study drug exposure will be summarized using descriptive statistics for patients in Phase 1 dose escalation phase and for patients in Phase 2a expansion phase by disease cohort at the MTD. Total duration of exposure to study drug in weeks will be calculated as the date of last dose minus the date of first dose plus one divided by 7, if there are no drug interruptions. If there are drug interruptions, the total duration will be determined minus the time of all drug interruptions. The number of weeks in all such cycles will be added within each dose cohort to calculate Total Duration of Exposure. Dose intensity (mg/m²/week) will be calculated as the total dose received per week during the cycle. The

total mg of drug received/week is calculated from the Volume Administered collected on the Study Drug Administration CRF page as follows: Total mg dose received = total mg dose prepared (mg/m² dose x BSA in m²) x (Volume Administered divided by total volume (mL) in which the drug dose was prepared), cumulative over Days 1, 8 and 15 of each cycle divided by 4 weeks (=1 cycle) for all Phase 1 patients, Phase 2a Cohort 10 (other cancer), 11 (cholangiocarcinoma), and 12 (gallbladder) patients. For Cohort 13 patients, the calculation will be based on cumulative doses over Days 1 and 8 of each cycle divided by 3 weeks (=1 cycle). Relative dose intensity will be calculated by dividing the Mean Dose Intensity per week by Total Dose Prescribed (in mg/week). For 'all other cycles', the Duration of Exposure, Dose Intensity, Relative Dose Intensity and Proportion of Patients <80% will be captured on a 'per cycle' basis (averaged across all subsequent cycles) and not as a cumulative sum of all subsequent cycles.

The details of study drug administration will be presented in a listing.

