8.4.2 Instructions Regarding Dose Delays and Dose Modifications

Adverse events considered for treatment interruption and dose reduction will exclude the events assessed by the investigator as exclusively related to underlying disease or medical condition/concomitant treatment. If treatment must be delayed for reasons other than toxicity, contact the Medical Monitor to discuss the reasons for delay and plans for resuming study therapy.

- Treatment may be delayed up to 14 days. If the patient has completed two cycles and, in the investigator's opinion, is receiving benefit, treatment may be delayed for longer than 14 days and then resumed following a discussion with the Medical Monitor. Patients who require the next treatment cycle to be held for more than 14 days due to ongoing toxicity from the prior cycle should have the dose reduced by 25%.

- Patients who experience a toxicity requiring reduction in dose level may continue treatment at the lower dose level until disease progression or unacceptable toxicity. The dose level may be reduced twice. Patients who continue to require dose modifications beyond this should be discontinued from the trial. Once the dose has been reduced it may not be escalated.
- See [APPENDIX C](#) for FF-10502-01 dose modification requirements.

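### Dose intensity is divided by the nominal cycle length, so time lost to cycle delays drops out of relative dose intensity and the proportion of patients below 80% can be understated

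*SAP*

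**What the plan says.** All the definitions are in SAP 3.4.1, Study Drug Administration.

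- Denominator for Phase 1 and Cohorts 10 to 12: dose is "cumulative over Days 1, 8 and 15 of each cycle divided by 4 weeks (=1 cycle"). For Cohort 13 it is "cumulative doses over Days 1 and 8 of each cycle divided by 3 weeks (=1 cycle"). Neither has a term for the length the cycle actually ran.
- Label: "Dose intensity (mg/m²/week) will be calculated as the total dose received per week during the cycle".
- Formula: "Total mg dose received = total mg dose prepared (mg/m² dose x BSA in m²"), multiplied by the fraction of the prepared volume that was infused.
- Relative measure: "Relative dose intensity will be calculated by dividing the Mean Dose Intensity per week by Total Dose Prescribed (in mg/week").
- Cycles in the all-other-cycles group: the "Proportion of Patients <80% will be captured on a 'per cycle' basis (averaged across all subsequent cycles").
- Duration of exposure: "If there are drug interruptions, the total duration will be determined minus the time of all drug interruptions".

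Protocol 8.4.2 states: "Treatment may be delayed up to 14 days". It permits longer delays, after discussion with the Medical Monitor, for patients who have completed two cycles and are benefiting. Appendix C includes routes by which dosing is held and then resumed at the full dose.

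**The concern.** Dose intensity is dose per unit of time. If the time is fixed at its planned value, the measure registers doses that were missed or cut but not doses that were given late. The protocol foresees full doses given late, because Appendix C lets some patients restart at 100% after a hold. For those patients relative dose intensity reads 100% however long the cycle ran. Duration of exposure does not recover the lost time either, where that time was recorded as an interruption and so subtracted.

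At stake is the exposure table. Relative dose intensity and the share of patients below 80% are the figures a reader would use to judge how closely the 90 mg/m² regimen was delivered on its two schedules. An error that only flatters delivery makes both less informative.

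**Working it through.** The SAP states no numerical dose intensity, so there is no planned figure to reproduce. The check applies its rule to the protocol's own regimens.

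**Inputs**

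- Cohorts 10 to 12: 90 mg/m², 3 doses per 28 days (Protocol 8.2).
- Cohort 13: 90 mg/m², 2 doses per 21 days (Protocol 8.2).
- Delay: up to 14 days (Protocol 8.4.2).
- Threshold: 80% (SAP 3.4.1).
- Convention: a delay counts in the cycle it prolongs, measured from first dose of that cycle to first dose of the next.

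**Planned intensity**

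- 28-day cycle: 90 × 3 / 4 = 67.5 mg/m²/week
- 21-day cycle: 90 × 2 / 3 = 60.0 mg/m²/week

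**All doses given in full, cycle prolonged by d days**

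SAP rule: (dose received / planned weeks) / planned intensity = 100% for any d.

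Actual time: dose received / (planned weeks + d/7) / planned intensity.

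| Delay | SAP rule | 28-day cycle, actual time | 21-day cycle, actual time |
|---|---|---|---|
| 0 days | 100% | 270/4 = 67.5 (100%) | 180/3 = 60.0 (100%) |
| 7 days | 100% | 270/5 = 54.0 (80.0%) | 180/4 = 45.0 (75.0%) |
| 14 days | 100% | 270/6 = 45.0 (66.7%) | 180/5 = 36.0 (60.0%) |

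**Delay at which one cycle reaches 80%**

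- 28/0.8 = 35 days, a delay of 7 days
- 21/0.8 = 26.25 days, a delay of 5.25 days

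Any longer delay puts that cycle below 80%, and the SAP rule does not show it.

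**Effect of averaging over later cycles**

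Mean of per-cycle values, with one 14-day delay and the other cycles on time:

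- 28-day: 66.7% over one cycle; (66.7 + 100)/2 = 83.3% over two; 88.9% over three.
- 21-day: 60.0% over one cycle; (60 + 100)/2 = 80.0% over two; 86.7% over three.

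So, with all doses otherwise full, one such delay moves a patient below 80% only where a single cycle is reported. Otherwise repeated delays are needed.

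**What the SAP rule still registers**

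- One omitted dose: 2/3 = 66.7% (28-day) or 1/2 = 50.0% (21-day).
- A partial infusion, through the volume administered.
- One 25% reduction: 75% if the reference is the assigned dose, but 100% if it is the reduced dose. The SAP does not say which applies.

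**Units**

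The formula gives mg/m² × m² × (mL/mL) = mg, and after division by weeks, mg/week. The stated denominator is also in mg/week, so the ratio is dimensionless. The mg/m²/week label on dose intensity itself does not match.

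**The case against.** Much can be said for the plan.

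- **Delays are not invisible.** SAP 3.4.2 summarises and lists adverse events that lead to drug interruption, and SAP 4.3 lists them again together with study drug administration. This stands. The gap is in the exposure statistics. A reader might infer that delay is reported nowhere, and the documents do not support that.
- **Interruption is not defined.** If a late cycle start is not recorded as a drug interruption, duration of exposure (last dose minus first dose plus one) includes it. This also stands: the subtraction hides only time that was recorded as interruption.
- **The 80% proportion is not wrong for every patient.** Omitted doses and partial infusions count, and averaging dilutes a single delay. A hold that ends in a skipped dose is captured. What remains is understatement for patients whose doses were given late, chiefly in a single reported cycle or with repeated delays.
- **The unit conflict need not affect the ratio.** A reader might infer that relative dose intensity divides mg/m²/week by mg/week, so that full dosing shows 1/BSA: 55.6% at an assumed 1.8 m², with a range of 66.7% to 45.5% over 1.5 to 2.2 m². The documents give no BSA, and the written formula never removes it from the numerator. Followed as written, the ratio is sound. The misreading would also raise the share below 80%, opposite to the delay effect.
- **No decision depends on it.** A reader might infer that the choice of RP2D is affected. Under Protocol 6.1 the MTD follows from counts of dose-limiting toxicity and becomes the RP2D. Relative dose intensity enters no MTD, futility or efficacy rule.

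None of this answers the fixed denominator, which gives the wrong value for a delayed cycle under the SAP's own definition of dose per week.

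**Conclusion.** The point holds for the time denominator. A fully dosed cycle delayed by 14 days scores 100% instead of 66.7% (28-day) or 60.0% (21-day), and the proportion of patients below 80% can be understated. These figures assume that all doses in the cycle were given in full and that the delay is counted in the cycle it prolongs. The documents give no frequency of delays, so the effect on the trial's summary cannot be calculated.

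Two secondary points are ambiguities rather than shown errors: the label on dose intensity disagrees with its formula, and the prescribed dose is not tied to either the assigned or the reduced dose. The measure is a descriptive exposure summary. It should be corrected before the tables are programmed, but no dose-finding or efficacy conclusion turns on it.

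**What to change.** In SAP 3.4.1:

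1. Divide each cycle's dose by its actual length in weeks, from first dose of the cycle to first dose of the next. State a rule for the last cycle, which has no next dose. Nominal length is one option, though it would still omit time lost in that cycle.
2. Use one unit in numerator and denominator. If mg/m²/week is kept, divide mg received by BSA. If mg/week is kept, change the label.
3. Define the reference as the originally assigned dose and schedule: assigned dose × 3/4 per week, or × 2/3 for Cohort 13.
4. Report duration of exposure including interruptions, define what counts as an interruption, and add a summary of the number and length of delays.

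The cost is a short SAP revision and minor reprogramming. Dose dates, volumes and BSA are already inputs to the SAP's calculations, so no new data are needed and no treatment rule changes. The downside is that relative dose intensity will look less favourable.

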3.4.2. Adverse Events

AEs reported from the date of the first dose of study drug to 28 days following the last dose of study drug will be presented. All AEs will be coded based on the Medical Dictionary for Regulatory Affairs (MedDRA; Version 17.0 or higher). An AE will be considered a treatment emergent adverse event (TEAE) if the onset is after the first dose of study drug or if the condition was present at baseline but worsened after the first dose.

All AEs for each patient will be listed, including intensity grading, relationship to study drug, action taken and outcome. Table summaries and patient listings of deaths, serious TEAEs, and TEAEs leading to treatment discontinuation will be provided.

TEAE summaries will be presented for patients in Phase 1 dose escalation phase and for patients in Phase 2a expansion phase by disease cohort. All TEAE summaries will show the number and percentage of patients experiencing at least 1 TEAE for each preferred term, arranged by system organ class, and the number of unique occurrences of the event. Separate summaries will be produced by relationship to study medication, and by severity, and for those events with an incidence of at least 2% in any group or overall. Patients with multiple events will be counted only once per SOC and preferred term. For each level of summarization, the event with the highest level of severity, or strongest drug relationship will be presented. TEAEs with Grade 3 or Grade 4 and drug-related TEAEs with Grade 3 or Grade 4 will be summarized. TEAEs leading to study drug interruption or discontinuation, Grade 3 and 4 TEAEs, Serious TEAEs will be summarized and also provided in a separate listing. In addition, a summary of TEAEs for the total occurrences of the events will be provided.

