10.1.6 Adverse Event Reporting

Each AE is to be reported by the investigator as serious or non-serious according to the definitions in Section 10.1.2 above. This classification determines the regulatory reporting procedures to be followed as described in Table 2.

Table 2. Reporting Guidelines for Adverse Events

Gravity of AE	Reporting Time to FPHU/Westat	Type of Report
Serious	Within 24 hours after the site becomes aware of the event	Initial SAE Report
Non-Serious	Per AE CRF module	Completed AE CRF Module

Any SAE, regardless of relationship to investigational therapy that occurs within 28 days following the last dose of study drug must be reported to the Medical Monitor within 24 hours after the site becomes aware of the event. The investigator is encouraged to discuss with the Medical Monitor any adverse experiences for which the issue of reportability is unclear or questioned. The initial report should be followed by submission of a more detailed SAE Report when follow-up information is available.

If the SAE occurs more than 28 days after the last dose of study drug, SAEs should be reported only if considered related to FF-10502-01. In the event of patient death, the reason for death should be recorded as the SAE, with 'death' recorded as the outcome on the SAE CRF module.

The SAE also will be recorded as an AE on the AE CRF module. Note: the SAE Report is different from the AE CRF. In areas of both forms where the same data are reported, the forms will be completed in a consistent manner. For example, the same term should be used for the AE on both forms, with the same start and stop dates, action taken, outcome, etc. A checkbox on the AE CRF module for whether the AE resulted in an SAE, will link the two types of report for a given event.

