11.3.1 Safety Analyses

11.3.1.1 Adverse Events

All safety endpoints will be summarized using descriptive statistics and will be based on the safety analysis dataset.

All AEs will be coded based on the Medical Dictionary for Regulatory Affairs (MedDRA; Version 15.0 or higher). An AE will be considered a treatment emergent adverse event (TEAE) if the onset is after the first dose of study drug to 28 days following the last dose of study drug or if the condition was present at baseline but worsened after the first dose.

All AEs for each patient will be listed, including intensity grading, relationship to study drug, action taken and outcome. Patient listings of deaths, SAEs, and AEs leading to treatment discontinuation will be provided. Patient narratives will be provided for deaths, SAEs and other significant AEs. Summary tables will be prepared to examine TEAE severity and relationship to study treatment.

AE summaries will be produced separately for each dose cohort and overall, and each disease cohort by dose and overall. All summaries will show, dose cohort and overall, the number and percentage of patients experiencing at least 1 TEAE of each preferred term, arranged by system organ class, and the number of occurrences of the event. Separate summaries will be produced by relationship to study drug, by severity, and for those events with an incidence rate of at least 2% in any group or overall.

SAEs will be summarized in a similar manner; overall, by relationship to study drug, and by severity.

In addition to the above, summaries of the number and percentage of patients discontinuing the study due to AEs and, due to death, will be presented.

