4.3. Mock Listings

The following listings will be presented in Phase 1 dose escalation phase and patients in Phase 2a expansion phase.

- Inclusion Criteria Not Met
- Exclusion Criteria Not Met
- Protocol Violations/Deviations/Exemptions
- Demographics
- End of Treatment
- End of Study
- Medical History
- Prior Cancer Therapy
- Radiation Therapy History
- Physical Examination
- Prior Medications
- Concomitant Medications
- Primary Diagnosis
- Study Drug Administration
- Pharmacokinetic (PK) Blood Sample Collection
- Pharmacodynamic (PD) Blood Sample Collection
- Screening Target Lesion Assessment (Non-Lymphoma Solid Tumor)
- Target Lesion Assessment (Non-Lymphoma Solid Tumor)
- Screening Non-Target Lesion Assessment (Non-Lymphoma Solid Tumor)
- Non-Target Lesion Assessment (Non-Lymphoma Solid Tumor)
- Tumor Biopsy Collection
- Disease Response Assessment (Non-Lymphoma Solid Tumor)
- Best Overall Disease Response Assessment
- Treatment Emergent Adverse Events (TEAEs)

- Serious Treatment Emergent Adverse Events
- Treatment Emergent Adverse Events Leading to Dose Adjustment, Temporary Interruption, or Permanent Discontinuation of Study Drug
- Treatment Emergent Adverse Events Leading to Permanent Discontinuation from Study
- Dose Limiting Toxicities
- Deaths
- Hematology
- Coagulation Parameters
- T Lymphocytes and B Lymphocytes
- Chemistry
- Urinalysis
- Vital Signs
- 12-lead Electrocardiogram
- Other Procedures
- Long Term Follow-up

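### Drug-related SAEs starting more than 28 days after the last dose are collected, but the SAP does not settle whether they are tabulated, and its stated window leaves them out

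*SAP*

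**What the plan says.** **Collection.** Protocol 10.1.4 ends the general AE reporting period 28 days after the last dose. Protocol 10.1.6 makes one exception: "If the SAE occurs more than 28 days after the last dose of study drug, SAEs should be reported only if considered related" to the study drug. The same section adds that "The SAE also will be recorded as an AE on the AE CRF module", with no time limit, so late related SAEs belong in the clinical database.

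**Definition of a TEAE.** Protocol 11.3.1.1 counts a new event "if the onset is after the first dose of study drug to 28 days following the last dose of study drug"; its second limb, for baseline conditions that worsen, carries no end date. SAP 3.4.2 counts an event "if the onset is after the first dose of study drug or if the condition was present at baseline" and then worsened. Neither limb of the SAP definition has an upper limit.

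**Presentation.** The first sentence of SAP 3.4.2 states: "AEs reported from the date of the first dose of study drug to 28 days following the last dose of study drug will be presented". It makes no exception for related SAEs.

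**Outputs.** Every AE table indexed in SAP 4.1.6.2 is built on TEAEs. In SAP 4.3 the AE listings are also TEAE-based, for example "Serious Treatment Emergent Adverse Events", apart from the listings of dose-limiting toxicities and deaths. Neither index has an output for late related SAEs.

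**Endpoint.** The statistical methods part of the protocol synopsis names the incidence of all SAEs as a safety endpoint alongside, and separate from, that of TEAEs. Protocol 11.3.1.1 plans SAE summaries by relationship and severity and does not word them as treatment-emergent only.

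**The concern.** The events that may fall out of the tables are a selected group. After day 28 an SAE is reported only if it has been attributed to the drug, so each event in this group is both serious and drug-related. Under the SAP's stated window, an unrelated SAE on day 20 after the last dose is tabulated and a related SAE on day 40 is not.

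The primary objective is the safety profile, and the tables of serious and drug-related events are where most readers will look for it. A programmer working from SAP 3.4.2 has a 28-day limit in one sentence and an open-ended definition two sentences later. Protocol 10.1.4, protocol 11.3.1.1 and the first sentence of SAP 3.4.2 all point to 28 days, so exclusion is a likely way for the plan to be carried out.

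The concern is with the analysis tables. It does not touch which events sites report or what halts recruitment.

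**Working it through.** The plan gives no figure to reproduce. The check takes one record, a non-fatal related SAE with onset on day 40 after the last dose, and follows it through each rule.

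| Rule | Source | Day-40 related SAE |
|---|---|---|
| Late SAE reporting | Protocol 10.1.6 | Reported, because related |
| Entry on the AE CRF | Protocol 10.1.6 | Entered |
| Presentation window | SAP 3.4.2, first sentence | Outside (40 > 28) |
| TEAE, new onset | Protocol 11.3.1.1 | Not a TEAE (40 > 28) |
| TEAE, new onset | SAP 3.4.2 | A TEAE (no upper limit) |
| SAE summaries, listing and narratives | Protocol 11.3.1.1 | Included as worded |
| Serious-event table and listing | SAP 4.1.6.2 and 4.3 | Depends on which rule governs |

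The last row has three branches:

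1. If the SAP presentation sentence governs, the event is in none of the SAP's AE or SAE tables.
2. If the protocol's TEAE definition is applied to the SAP's TEAE-only outputs, the result is the same.
3. If the SAP's TEAE definition governs and the presentation sentence is not applied as a filter, the event is in the serious, drug-related, severity and preferred-term tables.

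The documents do not say which branch applies.

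**Direction.** Incidence in a table row is x/n. Here n is the number of dosed patients in the safety population, which does not depend on the AE window, and x is the number of patients with a counted event. Let y be the number of patients whose only event for that row is a late related SAE. Including late events gives (x + y)/n, so leaving them out changes the reported rate by −y/n. This is zero or negative, never positive.

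**Weight of one patient.** With y = 1 and cohorts filled to their maximum:

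- Cohort 11: 1/50 = 2.0 percentage points
- Cohort 13: 1/27 = 3.7 points
- Cohort 10: 1/20 = 5.0 points
- Cohort 12: 1/10 = 10 points

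These are the most that one patient can move a row at those cohort sizes. SAP 3.4.2 counts a patient once per system organ class and preferred term, so a patient already in the row adds nothing. If a cohort enrols fewer patients than its maximum, 1/n is larger. The value of y is unknown.

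**The case against.** A reader might infer that every late related SAE is missing from the safety reporting. The documents do not support that:

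- The 28-day sentence in SAP 3.4.2 is a presentation window and not the TEAE rule. Under the SAP's own TEAE definition the event qualifies, so the fact that an output is restricted to TEAEs does not by itself exclude it.
- SAP 3.4.2 also says that all AEs will be listed for each patient, with relationship, although SAP 4.3 indexes only a TEAE listing.
- SAP 3.4.2 plans both a summary and a listing of deaths with no time limit, so a fatal case would not be confined to a listing.
- Protocol 11.3.1.1 plans SAE summaries, listings and narratives that are not limited to TEAEs.

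A reader might also take the PML stopping criterion in protocol 8.4.3 as showing that delayed toxicity is a declared concern of the study. That section and the PML risk history in protocol 9.1 deal with new cases and risk factors; neither says that onset after treatment is expected. Nor do the documents support any percentage of patients expected to have a late related SAE.

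There is also a fair argument against simple pooling. After day 28, unrelated SAEs and non-serious AEs fall outside routine collection, and the scheduled long-term contacts in protocol 9.5 are for survival. Late events are therefore found by a different and less complete route than earlier ones.

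All of this stands. It reduces the point from certain loss to undefined handling with a likely loss. It does not show where the events are to be tabulated, and it does not reconcile the SAP's serious-TEAE tables with the protocol's all-SAE endpoint.

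**Conclusion.** The point holds as a misalignment with a practical consequence. The collection rule, the SAP presentation window and the two TEAE definitions do not agree, and late related SAEs have no defined place in the SAP's tables. They are left out of the serious and drug-related tables if either the presentation window or the protocol's TEAE definition is applied, and in that case the SAP delivers less than the protocol endpoint. They are kept only if the SAP's open-ended definition overrides the sentence that opens its own section.

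Any error from omission lowers the reported incidence. Its size is zero if no such event occurs and cannot otherwise be estimated from the documents; the one-patient weights show scale only and assume full cohorts. The conclusion assumes that sites report and enter late related SAEs as protocol 10.1.6 requires. It should be settled before the tables are programmed.

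**What to change.** 1. Use one TEAE window in SAP 3.4.2 and protocol 11.3.1.1, and state whether it also applies to baseline conditions that worsen.
2. Extend the first sentence of SAP 3.4.2 so that it covers AEs up to 28 days after the last dose and, in addition, any SAE considered related to FF-10502-01 with later onset. Adding a clause to the SAP's TEAE definition alone would not be enough: that definition already admits these events, and it is the presentation sentence that removes them.
3. Show these events in the serious and drug-related summaries and in the SAE listing, flagged as onset after day 28. Because ascertainment differs after day 28, a separate line is an equally sound choice. Since the outputs in SAP 4.1.6.2 and 4.3 are titled as TEAE outputs, adjust the titles or footnotes so that the late events are not filtered out again.

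The cost is a sentence or two in each document, one more condition in the programmed flag, and a footnote. No new data are needed, and no reporting or clinical rule changes. The downside is that serious and related incidence may come out slightly higher.
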